9.7. Data Monitoring Committee

This study will not use a data monitoring committee (DMC). For the purpose of this protocol, Pfizer procedures for periodic safety review by a safety review team, comprised of the investigators and the sponsor, will be applied in order to review individual and summary data collected in the safety and clinical databases.

Discussions between the investigators and the sponsor regarding safety will occur in an ongoing manner at regular teleconferences and/or meetings to determine the safety profile and risk/benefit ratio and determine if further patient enrollment is appropriate.

10. QUALITY CONTROL AND QUALITY ASSURANCE

Pfizer or its agent will conduct periodic monitoring visits during study conduct to ensure that the protocol and Good Clinical Practices (GCPs) are being followed. The monitors may review source documents to confirm that the data recorded on CRFs are accurate. The investigator and institution will allow Pfizer monitors/auditors or its agents and appropriate regulatory authorities direct access to source documents to perform this verification. This verification may also occur after study completion.

During study conduct and/or after study completion, the investigator site may be subject to review by the IRB/EC, and/or to quality assurance audits performed by Pfizer, or companies working with or on behalf of Pfizer, and/or to inspection by appropriate regulatory authorities.

The investigator(s) will notify Pfizer or its agents immediately of any regulatory inspection notification in relation to the study. Furthermore, the investigator will cooperate with Pfizer or its agents to prepare the investigator site for the inspection and will allow Pfizer or its agent, whenever feasible, to be present during the inspection. The investigator site and investigator will promptly resolve any discrepancies that are identified between the study data and the patient's medical records. The investigator will promptly provide copies of the inspection findings to Pfizer or its agent. Before response submission to the regulatory authorities, the investigator will provide Pfizer or its agents with an opportunity to review and comment on responses to any such findings.

It is important that the investigator(s) and their relevant personnel are available during the monitoring visits and possible audits or inspections and that sufficient time is devoted to the process.

11. DATA HANDLING AND RECORD KEEPING

11.1. Case Report Forms/Electronic Data Record

As used in this protocol, the term CRF should be understood to refer to either a paper form or an electronic data record or both, depending on the data collection method used in this study.

A CRF is required and should be completed for each included patient. The completed original CRFs are the sole property of Pfizer and should not be made available in any form to third parties, except for authorized representatives of Pfizer or appropriate regulatory authorities, without written permission from Pfizer. The investigator shall ensure that the CRFs are securely stored at the study site in encrypted electronic form and will be password protected and/or secured in a locked room to prevent access by unauthorized third parties.

The investigator has ultimate responsibility for the collection and reporting of all clinical, safety, and laboratory data entered on the CRFs and any other data collection forms (source documents) and ensuring that they are accurate, authentic/original, attributable, complete, consistent, legible, timely (contemporaneous), enduring, and available when required. The CRFs must be signed by the investigator or by an authorized staff member to attest that the data contained on the CRFs are true. Any corrections to entries made in the CRFs or source documents must be dated, initialed, and explained (if necessary) and should not obscure the original entry.

In most cases, the source documents are the hospital or the physician's chart. In these cases, data collected on the CRFs must match the data in those charts.

In some cases, the CRF may also serve as the source document. In these cases, a document should be available at the investigator site and at Pfizer that clearly identifies those data that will be recorded on the CRF, and for which the CRF will stand as the source document.

11.2. Record Retention

To enable evaluations and/or inspections/audits from regulatory authorities or Pfizer, the investigator agrees to keep records, including the identity of all participating patients (sufficient information to link records, eg, CRFs and hospital records), all original signed informed consent documents, copies of all CRFs, safety reporting forms, source documents, and detailed records of treatment disposition, and adequate documentation of relevant correspondence (eg, letters, meeting minutes, and telephone call reports). The records should be retained by the investigator according to ICH guidelines, according to local regulations, or as specified in the clinical study agreement (CSA), whichever is longer. The investigator must ensure that the records continue to be stored securely for so long as they are retained.

If the investigator becomes unable for any reason to continue to retain study records for the required period (eg, retirement, relocation), Pfizer should be prospectively notified. The study records must be transferred to a designee acceptable to Pfizer, such as another investigator, another institution, or to an independent third party arranged by Pfizer.

Investigator records must be kept for a minimum of 15 years after completion or discontinuation of the study or for longer if required by applicable local regulations.

The investigator must obtain Pfizer's written permission before disposing of any records, even if retention requirements have been met.

12. ETHICS

12.1. Institutional Review Board/Ethics Committee

It is the responsibility of the investigator to have prospective approval of the study protocol, protocol amendments, informed consent documents, and other relevant documents, eg, recruitment advertisements, if applicable, from the IRB/EC. All correspondence with the IRB/EC should be retained in the investigator file. Copies of IRB/EC approvals should be forwarded to Pfizer.

The only circumstance in which an amendment may be initiated prior to IRB/EC approval is where the change is necessary to eliminate apparent immediate hazards to the patients. In that event, the investigator must notify the IRB/EC and Pfizer in writing immediately after the implementation.

12.2. Ethical Conduct of the Study

The study will be conducted in accordance with the protocol, legal and regulatory requirements and the general principles set forth in the International Ethical Guidelines for Biomedical Research Involving Human Subjects (Council for International Organizations of Medical Sciences 2002), ICH Guideline for Good Clinical Practice, and the Declaration of Helsinki.

12.3. Patient Information and Consent

All parties will comply with all applicable laws, including laws regarding the implementation of organizational and technical measures to ensure protection of patient personal data. Such measures will include omitting patient names or other directly identifiable data in any reports, publications, or other disclosures, except where required by applicable law.

The personal data will be stored at the study site in encrypted electronic and/or paper form and will be password protected or secured in a locked room to ensure that only authorized study staff have access. The study site will implement appropriate technical and organizational measures to ensure that the personal data can be recovered in the event of disaster. In the event of a potential personal data breach, the study site shall be responsible for determining whether a personal data breach has in fact occurred and, if so, providing breach notifications as required by law.

To protect the rights and freedoms of natural persons with regard to the processing of personal data, when study data are compiled for transfer to Pfizer and other authorized parties, patient names will be removed and will be replaced by a single, specific numerical code, based on a numbering system defined by Pfizer. All other identifiable data transferred to Pfizer or other authorized parties will be identified by this single, patient-specific code. The investigator site will maintain a confidential list of patients who participated in the study, linking each patient's numerical code to his or her actual identity. In case of data transfer, Pfizer will maintain high standards of confidentiality and protection of patients' personal data consistent with the Clinical Study Agreement and applicable privacy laws.

The informed consent documents and any patient recruitment materials must be in compliance with ICH GCP, local regulatory requirements, and legal requirements, including applicable privacy laws.

The informed consent documents used during the informed consent process and any patient recruitment materials must be reviewed and approved by Pfizer, approved by the IRB/EC before use, and available for inspection.

The investigator must ensure that each study patient is fully informed about the nature and objectives of the study, the sharing of data relating to the study and possible risks associated with participation, including the risks associated with the processing of the patient's personal data. The investigator further must ensure that each study patient is fully informed about his or her right to access and correct his or her personal data and to withdraw consent for the processing of his or her personal data.

The investigator, or a person designated by the investigator, will obtain written informed consent from each patient before any study-specific activity is performed [unless a waiver of informed consent has been granted by an IRB/EC]. The investigator will retain the original of each patient's signed consent document.

12.4. Reporting of Safety Issues and Serious Breaches of the Protocol or ICH GCP

In the event of any prohibition or restriction imposed (ie, clinical hold) by an applicable regulatory authority in any area of the world, or if the investigator is aware of any new information that might influence the evaluation of the benefits and risks of the investigational product, Pfizer should be informed immediately.

In addition, the investigator will inform Pfizer immediately of any urgent safety measures taken by the investigator to protect the study patients against any immediate hazard, and of any serious breaches of this protocol or of ICH GCP that the investigator becomes aware of.

13. DEFINITION OF END OF TRIAL

13.1. End of Trial in All Participating Countries

End of trial in all participating countries is defined as last patient last visit.

14. SPONSOR DISCONTINUATION CRITERIA

Premature termination of this study may occur because of a regulatory authority decision, change in opinion of the IRB/EC, or investigational product safety problems, or at the discretion of Pfizer. In addition, Pfizer retains the right to discontinue development of PF-06952229 at any time.

If a study is prematurely terminated, Pfizer will promptly notify the investigator. After notification, the investigator must contact all participating patients and the hospital pharmacy (if applicable) within 7 days. As directed by Pfizer, all study materials must be collected and all CRFs completed to the greatest extent possible.

15. PUBLICATION OF STUDY RESULTS

15.1. Communication of Results by Pfizer

Pfizer fulfills its commitment to publicly disclose clinical trial results through posting the results of studies on www.clinicaltrials.gov (ClinicalTrials.gov), the European Clinical Trials Database (EudraCT), and or www.pfizer.com, and other public registries in accordance with applicable local laws/regulations.

In all cases, study results are reported by Pfizer in an objective, accurate, balanced, and complete manner and are reported regardless of the outcome of the study or the country in which the study was conducted.

www.clinicaltrials.gov

Pfizer posts clinical trial US Basic Results on www.clinicaltrials.gov for Pfizer-sponsored interventional studies (conducted in patients) that evaluate the safety and/or efficacy of a Pfizer product, regardless of the geographical location in which the study is conducted. US Basic Results are submitted for posting within 1 year of the primary completion date (PCD) for studies in adult populations or within 6 months of the PCD for studies in pediatric populations.

PCD is defined as the date that the final patient was examined or received an intervention for the purposes of final collection of data for the primary outcome, whether the clinical study concluded according to the prespecified protocol or was terminated.

EudraCT

Pfizer posts European Union (EU) Basic Results on EudraCT for all Pfizer-sponsored interventional studies that are in scope of EU requirements. EU Basic Results are submitted for posting within 1 year of the PCD for studies in adult populations or within 6 months of the PCD for studies in pediatric populations.

www.pfizer.com

Pfizer posts Public Disclosure Synopses (CSR synopses in which any data that could be used to identify individual patients has been removed) on www.pfizer.com for Pfizer-sponsored interventional studies at the same time the US Basic Results document is posted to www.clinicaltrials.gov.

15.2. Publications by Investigators

Pfizer supports the exercise of academic freedom and has no objection to publication by the principal investigator (PI) of the results of the study based on information collected or generated by the PI, whether or not the results are favorable to the Pfizer product. However, to ensure against inadvertent disclosure of confidential information or unprotected inventions, the investigator will provide Pfizer an opportunity to review any proposed publication or other type of disclosure of the results of the study (collectively, "publication") before it is submitted or otherwise disclosed.

The investigator will provide any publication to Pfizer at least 30 days before it is submitted for publication or otherwise disclosed. If any patent action is required to protect intellectual property rights, the investigator agrees to delay the disclosure for a period not to exceed an additional 60 days.

The investigator will, on request, remove any previously undisclosed confidential information before disclosure, except for any study- or Pfizer product-related information necessary to the appropriate scientific presentation or understanding of the study results.

If the study is part of a multicenter study, the investigator agrees that the first publication is to be a joint publication covering all investigator sites, and that any subsequent publications by the PI will reference that primary publication. However, if a joint manuscript has not been submitted for publication within 12 months of completion or termination of the study at all participating sites, the investigator is free to publish separately, subject to the other requirements of this section.

For all publications relating to the study, the institution will comply with recognized ethical standards concerning publications and authorship, including Section II - "Ethical Considerations in the Conduct and Reporting of Research" of the Uniform Requirements for Manuscripts Submitted to Biomedical Journals, http://www.icmje.org/index.html#authorship, established by the International Committee of Medical Journal Editors.

Publication of study results is also provided for in the CSA between Pfizer and the institution. In this section entitled Publications by Investigators, the defined terms shall have the meanings given to them in the CSA.

If there is any conflict between the CSA and any attachments to it, the terms of the CSA control. If there is any conflict between this protocol and the CSA, this protocol will control as to any issue regarding treatment of study patients, and the CSA will control as to all other issues.

Appendix 1. ABBREVIATION LIST

Abbreviation	Term
ADME	absorption, distribution, metabolism, and excretion
ADTs	androgen depleting therapies
AE	adverse event
Ae%	percent of the cumulative amount of unchanged drug excreted
	into the urine
AIDS	acquired immunodeficiency syndrome
ALP	alkaline phosphatase
ALT	alanine aminotransferase
anti HBc	hepatitis B core antibody
anti HBs	hepatitis B surface antibody
ANC	absolute neutrophil count
ANOVA	analysis of variance
ARA	acid reducing agent
ASCO	American Society of Clinical Oncology
AST	aspartate aminotransferase
ATD	Accelerated Titration Design
AUC _{24h}	area under the concentration-time curve from time 0 to
	24 hours after dose
AUC _{inf}	area under the plasma concentration versus time curve from
	time 0 extrapolated to infinity
AUC _{last}	area under the plasma concentration versus time curve from
	0 to last
$AUC_{ss,\tau}$	area under the plasma concentration curve at time of steady
,	state
$AUC_{sd,\tau}$	area under the plasma concentration curve at standard
,	deviation
BBS	Biospecimen Banking System
BID	twice daily
BNP	B-type natriuretic peptide
BP	blood pressure
BUN	blood urea nitrogen
C#D#	Cycle # Day #
CA 15-3	cancer antigen 15-3
Cavg	average concentration
C _{max}	maximum plasma concentration
C_{min}	minimum plasma concentration,
CD	compact disc
CD4	cluster of differentiation 4
CD8	cluster of differentiation 8
CDK	cyclin dependent kinase
CEA	carcinoembryonic antigen

Abbreviation	Term
Ceff	effective concentration
CI	confidence interval
CK	creatine kinase
CLb	predicted blood clearance
CL/F	apparent clearance
CL _{ss} /F	steady state apparent clearance
CL_R	renal clearance of the drug from plasma
CNS	central nervous system
COVID-19	coronavirus disease 2019
CR	complete response
CRF	case report form
CRPC	castration-resistant prostate cancer
CSA	clinical study agreement
CSR	clinical study report
Css,max	steady state maximum plasma concentration
Css,min	steady state minimum plasma concentration
CT	computed tomography
CTA	clinical trial application
CCI	
CTCAE	Common Terminology Criteria for Adverse Events
CV	coefficient of variation
CYP	cytochrome
DDI	drug-drug interaction
DHT	Dihydrotestosterone
DICOM	digital imaging and communications in medicine
DILI	drug-induced liver injury
DL	dose level
DLT	dose-limiting toxicity
CCI	
DoR	duration of response
DRF	Dose-range finding
DVD	digital versatile disc
DVT	deep venous thrombosis
EC	ethics committee
EC ₅₀	concentration corresponding to 50% of the maximum effect
ECG	Electrocardiogram
ECOG	Eastern Cooperative Oncology Group
EDP	exposure during pregnancy
EDV	end diastolic volume
Eg	for example
EMT	epithelial-to-mesenchymal transition
EOT	end of treatment

Abbreviation	Term
1 Abbi C viacion	Term
ER	estrogen receptor
ERK	extracellular signal-regulated kinase
ESA	erythropoiesis stimulating agents
ESV	end systolic volume
EU	European Union
EudraCT	European Clinical Trials Database
F	Bioavailability (systemic availability of the administered dose)
Fa	fraction absorbed
FDA	Food and Drug Administration
FDG	Fluorodeoxyglucose
CCI	
FIH	first in human
FIP	First-in-patient
FSH	follicle-stimulating hormone
FTP	file transfer protocol
GCP	Good Clinical Practice
GI	Gastrointestinal
GGT	gamma-glutamyl transferase
GLP	Good Laboratory Practice
GnRH	gonadotropin-releasing hormone agonist
HBsAg	hepatitis B virus surface antigen
HbcAb	hepatitis B core antibody
HCVAb	hepatitis C virus antibodies
HBV	hepatitis B virus
HCV	hepatitis C virus
HER2	human epidermal growth factor receptor 2
hERG	human ether à-go-go-related gene
HIV	human immunodeficiency virus
HNSCC	squamous cell cancer of the head and neck
HNSTD	highest non-severely toxic dose
HR	heart rate
HR+	hormone receptor positive
hs-CRP	high-sensitivity C-reactive protein
5-HT	5-hydroxytryptamine
HTTP	hypertext transfer protocol
IB	investigator's brochure
IC50	50% inhibitive concentration
ICH	International Conference on Harmonisation
ID	Identification
Ie	that is
IHC	Immunohistochemistry
IL-2	Interleukin-2

Abbreviation	Term
IND	investigational new drug
INR	international normalized ratio
IP	investigational product
IRB	Institutional Review Board
IRF	independent radiology facility
IUD	intrauterine device
IVC	abdominal imaging at 60 to 70% after intravenous
	administration of contrast material
JNK	c-jun N-terminal kinase
Ka	absorption rate
K ₂ EDTA	dipotassium ethylenediaminetetraacetic acid
LFT	liver function test
LHRH	luteinizing hormone releasing hormone
LVEF	left ventricular ejection fraction
MAP	mitogen-activated protein kinase
mBC	metastatic breast cancer
mCRPC	metastatic castration-resistant prostate cancer
mITT	modified intent to treat
mTPI	modified target probability interval
MD	multiple dose
MDP	methylene diphosphonate
MedDRA	Medical Dictionary for Regulatory Activities
MRI	magnetic resonance imaging
MTD	maximum tolerated dose
N/A	not applicable
NCA	non-compartmental analysis
NCCN	National Comprehensive Cancer Network
NCI	National Cancer Institute
NK	natural killer
OS	overall survival
ORR	objective response rate
PACL	Protocol Administrative Change Letter
PBPK	physiologically based pharmacokinetic
PI3K	phosphatidylinositol-4,5-bisphosphate 3-kinase
pT	target probability
PCD	primary completion date
PCWG2	Prostate Cancer Working Group 2
PD	pharmacodynamics; progressive disease
PD-1	programmed cell death
PD-L1	programmed death ligand - 1
PE	physical examination
PEG 400	polyethylene glycol 400

Abbreviation	Term
PET	positron emission tomography
PFS	progression-free survival
PD-L1/PD-1	programmed death-ligand 1/ programmed cell death protein 1
PI	principal investigator
PK	pharmacokinetic
PO	administered orally
PPI	proton pump inhibitor
PR	pulse rate; partial response
PS	performance status
PSA	prostate specific antigen
pSMAD2	phosphorylated mothers against decapentaplegic homolog 2
PT	prothrombin time
PTT	partial thromboplastin time
QD	once daily
QT	time between the start of the Q wave and the end of the T wave
QTcF	Fridericia's QTc correction formula
QTcB	Bazett's QTc correction
Rac	accumulation ratio
RECIST	Response Evaluation Criteria in Solid Tumors
RANK	Receptor activator of nucleus factor kappa B-ligand
RNA	ribonucleic acid
RP2D	recommended Phase 2 dose
RR	respiratory rate
R_{ss}	linearity ratio
RUQ	right upper quadrant
SAE	serious adverse event
SAP	statistical analysis plan
SARS-CoV-2	severe acute respiratory syndrome coronavirus 2
SCLC	small cell lung cancer
SLE	systemic lupus erythematosus
SOA	schedule of activities
SOC	standard of care
SOP	standard operating procedure
SRSD	single reference safety document
STD	severely toxic dose
STD ₁₀	severely toxic dose in 10% of the animals
t½	terminal elimination half-life
TBili	total bilirubin
TBNK	T-cells, B-cells, Natural Killer cells
TDI	time dependent inhibition
TGFβ	transforming growth factor beta
TGFβR1	transforming growth factor beta receptor 1

Abbreviation	Term
TGI	tumor growth inhibition
T _{max}	time to maximum plasma concentration
TME	tumor microenvironment
$T_{ss,max}$	time to steady-state maximum plasma concentration
TTP	time to progression
TTR	time to response
ULN	upper limit of normal
UPM	unit probability mass
US	United States
USPI	United States Package Insert
UVB	ultraviolet B
Vd/F	apparent volume of distribution after non-intravenous
	administration
Vd_{ss}	steady-state volume of distribution
V _{ss} /F	apparent volume of distribution at steady state after
	non-intravenous distribution
V _z /F	Apparent volume of distribution during terminal phase after
	non-intravenous administration
WBC	white blood cell

Appendix 2. Detailed Dose Escalation/De-Escalation Scheme for mTPI design

DLT	n=1	n=2	n=3	n=4	n=5	n=6	n=7	n=8	n=9	n=10	n=11	n=12
0	E	E	E	E	E	E	E	E	E	E	E	E
1	D	S	S	S	S	S	Е	Е	Е	Е	Е	E
2		DU	D	D	S	S	S	S	S	S	S	E
3			DU	DU	D	D	S	S	S	S	S	S
4				DU	DU	DU	DU	D	S	S	S	S
5					DU	DU	DU	DU	DU	D	S	S
6						DU	DU	DU	DU	DU	DU	DU
7							DU	DU	DU	DU	DU	DU
8								DU	DU	DU	DU	DU
9									DU	DU	DU	DU
10										DU	DU	DU
11											DU	DU
12												DU

Source: https://udesign.laiyaconsulting.com/.

E: Escalate to the next higher dose; S: Stay at the same dose; D: De-escalate to the previous lower dose; DU: De-escalate to the previous lower dose and the current dose will never be used again in the trial.

Escalation/De-escalation algorithms for total number of patients treated at the current dose level (current and previous cohorts)

- With 2 patients treated at current dose level:
 - 0 DLT -> escalate;
 - 1 DLT -> remain at the same dose;
 - 2 DLTs -> de-escalate and consider current dose as intolerable.
- With 3 patients treated at current dose level:
 - 0 DLT -> escalate;
 - 1 DLT -> remain at the same dose;
 - 2 DLTs -> de-escalate;
 - 3 DLTs -> de-escalate and consider current dose as intolerable.
- With 4 patients treated at current dose level:
 - 0 DLT -> escalate;
 - 1 DLT -> remain at the same dose;

- 2 DLT -> de-escalate;
- 3-4 DLTs -> de-escalate and consider current dose as intolerable.
- With 5 patients treated at current dose level:
 - 0 DLT -> escalate;
 - 1-2 DLTs -> remain at the same dose;
 - 3 DLTs -> de-escalate;
 - 4-5 DLTs -> de-escalate and consider current dose as intolerable.
- With 6 patients treated at current dose level:
 - 0 DLT -> escalate;
 - 1-2 DLT -> remain at the same dose;
 - 3 DLTs -> de-escalate;
 - 4-6 DLTs -> de-escalate and consider current dose as intolerable.
- With 7 patients treated at current dose level:
 - 0-1 DLT -> escalate;
 - 2-3 DLTs -> remain at the same dose;
 - 4-7 DLTs -> de-escalate and consider current dose as intolerable.
- With 8 patients treated at current dose level:
 - 0-1 DLT -> escalate;
 - 2-3 DLTs -> remain at the same dose;
 - 4 DLTs -> de-escalate;
 - 5-8 DLTs -> de-escalate and consider current dose as intolerable.
- With 9 patients treated at current dose level:
 - 0-1 DLT -> escalate;
 - 2-4 DLTs -> remain at the same dose;

- 5-9 DLTs -> de-escalate and consider current dose as intolerable.
- With 10 patients treated at current dose level:
 - 0-1 DLT -> escalate;
 - 2-4 DLTs -> remain at the same dose;
 - 5 DLTs -> de-escalate;
 - 6-10 DLTs -> de-escalate and consider current dose as intolerable.
- With 11 patients treated at current dose level:
 - 0-1 DLT -> escalate;
 - 2-5 DLTs -> remain at the same dose;
 - 6-11 DLTs -> de-escalate and consider current dose as intolerable.
- With 12 patients treated at current dose level:
 - 0-2 DLTs -> escalate;
 - 3-5 DLTs -> remain at the same dose;
 - 6-12 DLTs -> de-escalate and consider current dose as intolerable.

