3.1.1.4. Standard (mTPI) Escalation Phase

The proposed mTPI method for this protocol includes stopping rules and dose escalation/finding criteria which prevent the target DLT rate to reach ≥33% for determining the MTD. Targeting a DLT rate of 27.5% and an acceptable DLT interval (22.5% to 32.5%) will be utilized in both Parts 1A – Monotherapy Dose Escalation (beginning at Dose Level 5) and 1B – Combination Dose Escalation, and will also be used to monitor the DLTs so as not to cross toxicity boundaries in the expansion of a cohort. At least 3 DLT-evaluable patients will be required for the dose escalation decision based on mTPI beginning at Dose Level 5. Note provided the DLT rate for cardiac toxicity does not exceed 10%. The decision rules use a Beta (1,1) prior.

Table 2. mTPI Dose Decision Rules

DLT	n=1	n=2	n=3	n=4	n=5	n=6	n=7	n=8	n=9	n=10	n=11	n=12
0	Е	Е	Е	Е	Е	Е	Е	Е	Е	Е	Е	Е
1	D	S	S	S	S	S	Е	Е	Е	E	Е	Е
2		DU	D	D	S	S	S	S	S	S	S	Е
3			DU	DU	D	D	S	S	S	S	S	S
4				DU	DU	DU	DU	D	S	S	S	S
5					DU	DU	DU	DU	DU	D	S	S
6						DU	DU	DU	DU	DU	DU	DU
7							DU	DU	DU	DU	DU	DU
8								DU	DU	DU	DU	DU
9									DU	DU	DU	DU
10										DU	DU	DU
11											DU	DU
12												DU

Source: https://udesign.laiyaconsulting.com/

E: Escalate to the next higher dose; S: Stay at the same dose; D: De-escalate to the previous lower dose; DU: De-escalate to the previous lower dose and the current dose will never be used again in the trial.

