3.3. MTD Definition

A DLT rate of 27.5% with an equivalence interval of (22.5%, 32.5%) (note: provided the DLT rate for cardiac toxicity does not exceed 10%) will be utilized to estimate the MTD; patients will be enrolled in dose cohorts of 2-4 patients, and each patient will receive 2 courses of PF-06952229 (7 days on, 7 days off) in a 28 day cycle. Due to the discreteness of the dose levels and in the interest of the safety of patients, the estimated MTD is the highest tested dose level with DLT rate ≤ approximately 32.5%. The dose finding decision will be based on a 1-cycle (28 day) DLT observation period.

At least 6 patients have been accumulated on a dose that can be predicted to be the MTD.

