9.2. Statistical Methods and Properties

9.2.1. Statistical Methods for Dose Escalation

This study contains 2 parts, dose escalation with PF-06952229 (Part 1A), followed by dose escalation for PF-06952229 in combination with enzalutamide (Part 1B), and dose expansion for PF-06952229 as a monotherapy (Part 2A) and combination dose expansion of PF-06952229 with enzalutamide in patients with mCRPC (Part 2B).

Part 1A Single Agent PF-06952229 and Part 1B PF-06952229 Plus Enzalutamide Combination Dose Escalation

The dose escalation in Part 1A will start with Accelerated Titration Design (ATD) as proposed by Simon et al (Journal of the National Cancer Institute, Vol. 89, No. 15, August 6, 1997). Part 1 will have an initial accelerated phase followed by a standard (mTPI) escalation phase. During the accelerated phase, initial cohorts to contain a minimum of one patient until the first instance of first-cycle CTCAE grade ≥2 toxicity.

The traditional mTPI design⁴ uses a Bayesian statistics framework and a beta/binomial hierarchical model to compute the posterior probability of 3 dosing intervals that reflect the relative difference between the toxicity rate of each dose level to the target rate (pT = 0.275). If the toxicity rate of the currently used dose level is far smaller than pT, the mTPI will recommend escalating the dose level; if it is close to target probability (pT), the mTPI will recommend continuing at the current dose; if it is far greater than pT, the mTPI will recommend de-escalating the dose level. These rules are conceptually similar to those used by the 3+3 design, except the decisions of an mTPI design are based on posterior probabilities calculated under a coherent probability model. The proposed mTPI method for this protocol includes stopping rules and dose escalation criteria, which prevents the target DLT rate to reach \geq 33% for determining the MTD. This proposed mTPI method is more conservative than the traditional TPI method.

Decision rules are based on calculating unit probability mass (UPM) of 3 dosing intervals corresponding to under, proper, and over dosing in terms of toxicity. Specifically, the underdosing interval is defined as (0; pT-e1), the over-dosing interval (pT+e2, 1), and the proper-dosing interval (pT- e1, pT+ e2), where e1 and e2 are small fractions. Therefore, the target interval for the DLT rate is (0.225, 0.325).

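### Table 2 and Appendix 2 say Stay at 4/9, 4/10, 4/11 and 5/11, adding patients to a dose that can no longer be chosen as MTD within 12 patients

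*Protocol*

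**What the plan says.** **The grid.** Table 2 (protocol Section 3.1.1.4) and Appendix 2 give the decision for each DLT count at n = 1 to 12. In Appendix 2 the entry at n = 9 and at n = 10 is "2-4 DLTs -> remain at the same dose", and at n = 11 it is "2-5 DLTs -> remain at the same dose". At n = 12, counts of 3 to 5 also mean Stay. The neighbouring cells 4/8 and 5/10 are De-escalate (D).

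**The ceiling.** Section 3.1.1.4 says the method has stopping rules and dose-finding criteria that "prevent the target DLT rate to reach ≥33% for determining the MTD". It adds that the 27.5% target and the 22.5–32.5% interval "will also be used to monitor the DLTs so as not to cross toxicity boundaries in the expansion of a cohort". Section 3.3 says "the estimated MTD is the highest tested dose level with DLT rate ≤ approximately 32.5" percent. Section 9.2.2 and SAP 5.2.2 go further: they name 4 out of 10 as a result that rules a dose out as MTD, and acknowledge that mTPI alone might permit it. Section 9.2.1 says: "This proposed mTPI method is more conservative than the traditional TPI method".

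**Numbers.** Section 9.6.1 says the patients treated at a dose will range from 1 to 12. Section 3.3 says "patients will be enrolled in dose cohorts of 2-4 patients".

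**The concern.** The ceiling is stated for choosing the MTD, but nothing says what to do with the next cohort once a dose can no longer meet it. In that position the printed grid says Stay. The clearest case is 4/10: Section 9.2.2 uses it as its example of a dose that cannot be the MTD, while Appendix 2 directs further enrolment there. The grid is also uneven. It says D at 4/8, but one more patient without a DLT turns D into Stay, although the dose is still out of reach of the ceiling. At stake are a few patients treated at a dose with an observed DLT rate of 36–45% when their data cannot make that dose eligible.

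**Working it through.** **Inputs.** Target 0.275 and interval (0.225, 0.325): Section 9.2.1. Prior Beta(1,1): Section 3.1.1.4. Prior Beta(0.5,0.5) and exclusion threshold 0.95: Section 9.2.2. Maximum of 12 per dose: Section 9.6.1. Cohorts of 2 to 4: Section 3.3.

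**1. Reproduce the grid.** With x DLTs in n patients and prior Beta(a,a), the posterior is Beta(a+x, a+n−x). For each interval, the unit probability mass is posterior probability divided by length; the largest decides. D becomes DU (the dose is excluded for good) when P(rate > 0.275) exceeds 0.95. Beta(1,1) reproduces all 90 printed cells, so the grid is unmodified mTPI output. Beta(0.5,0.5) differs only at 2/4, 1/5, 1/6 and 2/11. The cells at issue are Stay under both priors.

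**2. Best attainable final rate**, with no further DLT up to n = 12:

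| Cell | Observed | Best at n = 12 | P(rate > 0.275), Beta(1,1) | Patients still to come |
|---|---|---|---|---|
| 4/9 | 44.4% | 4/12 = 33.3% | 0.889 | 3 |
| 4/10 | 40.0% | 33.3% | 0.841 | 2 |
| 4/11 | 36.4% | 33.3% | 0.787 | 1 |
| 5/11 | 45.5% | 5/12 = 41.7% | 0.918 | 1 |

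Every other Stay cell below n = 12 has at most 3 DLTs, so 3/12 = 25% or less remains attainable. Four DLTs need n = 13 (4/13 = 30.8%) and five need n = 16 (5/16 = 31.3%) to come within 32.5%. The cells 4/12 and 5/12 are also Stay, which would mean a 13th patient.

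**3. Chance of being told to Stay in one of the four cells**, during one continuous stay at a dose, true rate p, q = 1 − p:

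- *Cohorts of 3.* The only route is 1/3, then 1/6 or 2/6, then 4/9: 3pq² × [q³·p³ + 3pq²·3p²q] = 30p⁴q⁵. For p = 0.25, 0.30, 0.35, 0.40, 0.45, 0.50 this is 2.8, 4.1, 5.2, 6.0, 6.2, 5.9%. Each occurrence adds 3 patients.
- *Cohorts of 2.* The route is 1/2, 1/4, then 1/6 or 2/6, then 2/8 or 3/8, then 4/10: 2pq³ × [4pq³·p² + 5p²q²·2pq] = 28p⁴q⁶, or 1.9–3.3% over the same range, with 2 more patients. This reads the grid at n = 2. Section 3.1.1.4 requires 3 evaluable patients for an escalation decision. If the 0/2 result therefore waits for the second pair, 1/4 has probability 4pq³ instead of 2pq³ and the figure doubles to 3.9–6.7%.
- *Cohorts of 4.* Zero: n goes 4, 8, 12, and 4/8 is D.
- *Mixed cohorts of 2 to 4, first cohort 3 or 4.* By exact enumeration, the 19 sequences that fill exactly 12 range from 0 to 10.7% (the maximum is 3, 4, 3, 2 at p = 0.40). The 13 that pass through n = 11 reach at most 18.9% (3, 2, 4, 2 at p = 0.40). The documents give no basis for weighting these sequences, so no average is offered.

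**The case against.** **The sponsor foresaw this.** Section 9.2.2 bars such doses as MTD, and the 33% wording concerns determining the MTD rather than allocation. The clause about cohort expansion states no observed-rate stop and could refer to expanding a dose already selected. This stands in part. No wrong MTD follows, and the grid has no arithmetic error. What remains is that no text says where the next cohort goes.

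**The premise is conditional.** The 12-patient figure sits in a sample-size description rather than an enrolment rule, and Section 3.1 allows patients to be added to doses below the MTD. Beyond 12, four DLTs could still qualify. The word approximately in Section 3.3 could also admit 33.3%. Both points are fair. Against them, no decision rule is printed beyond n = 12, 33.3% breaches the explicit 33% limit in Section 3.1.1.4, and 5/11 fails on either reading of the ceiling.

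**The sponsor can override.** Written dose assignment (Section 5.1) and regular safety discussions (Section 9.7) allow judgement, but prescribe nothing for these cells.

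**Stronger readings to resist.** A reader might infer that the plan could select an overly toxic dose; Section 9.2.2 prevents that. A reader might also turn the per-dose chances into a share of trials affected. That depends on assumed dose-toxicity curves and on how the stop at 6–12 patients at the predicted MTD is read, neither of which the documents settle. Finally, the cardiac sentence in Section 3.1.1.4, "Note provided the DLT rate for cardiac toxicity does not exceed 10" percent, is incomplete and might suggest a rule closing a dose after two cardiac DLTs. The documents give no cardiac DLT rate to calibrate one, Section 3.3 ties the proviso to MTD estimation, and Sections 1.5.2.1 and 5.4.4 already take affected patients off treatment. No such rule is proposed.

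**Conclusion.** The point holds as a gap in allocation, not in MTD selection. In four cells the grid enrols 1 to 3 more patients at a dose that can no longer become the MTD, and 4/12 and 5/12 would continue past the stated maximum. For true DLT rates of 25–50%, the chance per dose is about 3–6% with cohorts of 3, about 2–3% with cohorts of 2 read after every pair, and zero with fixed cohorts of 4; some mixed sequences give more. It rests on two assumptions: at most 12 patients per dose, and 33.3% failing the ceiling. The cells 5/11 and 5/12 need only the first. Low severity: a cheap improvement for patient safety that makes allocation agree with the sponsor's own limit.

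**What to change.** - **Table 2:** change 4/9, 4/10, 4/11, 5/11, 4/12 and 5/12 from S to D.
- **Appendix 2:** n = 9, 2–3 DLTs remain and 4 de-escalate; n = 10 and n = 11, 2–3 remain and 4–5 de-escalate; n = 12, 3 remain and 4–5 de-escalate. The DU entries stay as printed.
- **Footnote to both:** a dose with 4 or more DLTs receives no further patients, because it cannot meet the MTD ceiling within 12 patients; Escalate from the dose below then means Stay.
- **Section 9.2.2 and SAP 5.2.2, one line each:** this closure is separate from the 0.95 exclusion rule and also applies to the existing D cells 4/8 and 5/10. Without this line, a later Escalate from the dose below could reopen those doses.

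The cost is six cells, four Appendix 2 entries, one footnote and two sentences, with no new procedures. The downside is that borderline doses close slightly earlier, at a posterior probability of exceeding 27.5% that is below 0.95: under Beta(1,1), from 0.727 at 4/12 to 0.947 at 5/10. That is why the closure needs its own line and should not be presented as part of the 0.95 rule.
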